8.0 Criteria for Evaluation and Endpoint Definitions

Outcome Measures

The primary outcome measure will be rotator cuff healing as measured by the MRI Sugaya classification.^{6,7} Measures will be performed at 12 weeks (the conclusion of Oxandrolone vs. placebo treatment), 6 months, 1 year and 2 years follow-up. The primary end-point will be 6 months.

Secondary outcome measures will include:

- 1) MRI evidence of rotator cuff fatty infiltration and muscle volume.
- 2) Patient-reported outcomes will be assessed with the ASES, a VAS, and PASS questionnaire.
- 3) Functional outcome will be assessed with shoulder range of motion with goniometer and isometric shoulder strength measures using a handheld dynamometer
- 4) Lean body mass and fat will be assessed with bioelectric impedance.

9.0 Data Collection and Monitoring

The research coordinator, employed by the Department of Orthopaedic Surgery, will be responsible for patient enrollment and data collection. Source documents will be stored in an office in a locked cabinet within the Department of Orthopaedic Surgery. Data will also be collected and stored using CTSI RedCap.

10.0 Statistical Considerations

Statistical Methods

Descriptive statistics will be performed for participant demographics, historical information, intraoperative variables, as well as baseline testosterone, MRI measures of rotator cuff integrity, rotator cuff fatty infiltrate, rotator cuff muscle volume, shoulder strength, shoulder range of motion, patient-rated outcomes and body composition. Comparison for the primary outcome measure of rotator cuff integrity between groups from baseline to 1 year (primary endpoint) will be performed using a repeated measures analysis of Generalized Estimating Equation (GEE), appropriate for ordinal data. The GEE will also be used to compare between groups over time for the secondary outcome of fatty infiltrate (ordinal data). For all other secondary outcome variables, we will also use GEE for linear regression (ordinal data) or mixed model (continuous data) with repeatedly measured outcomes. Significance level will be established as $p < 0.05$. Analyses will be performed using STATA 13 software (College Station, TX) or SPSS and in consultation with the Statistics Department at USC.

Power Analysis and Sample Size

A power analysis for a sample size estimation was performed to detect a difference of 1 Sugaya grade (1-5 grades) classification (primary outcome) between the experimental and control group using 3 repeated measurements (baseline, 12 week, and 6 months).¹⁴ The power analysis was based with 2-sided alpha = 0.05 and power of 80%, and assuming a correlation among the repeated measures of 0.7 and overall SD of 2, giving a minimum sample size of 104 participants (n=52 participants in each group). This corresponds to an ANOVA effect size of 0.28 (28% of variance in primary outcome explained by treatment effect), or alternatively a moderate Cohen's D effect size (group mean difference divided by SD) of 0.5. Oversampling by 10% to account for possible attrition yields a total of 116 participants with 58 per group.

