3.0 Study Design

Trial Design

This is a single-center, prospective 1:1 double blind randomized control trial. The trial will be conducted at the University of Southern California (USC), Keck School of Medicine in Los Angeles, California. Patients will be recruited from the Department of Orthopaedics. Men and women, 40–75 years of age, with MRI proven rotator cuff tears, indicated and scheduled for repair will be eligible for inclusion. Men and women with acute tears and those with significant comorbid liver, lung, cardiac, and kidney conditions will be excluded. Women who are pregnant or nursing will also be excluded. Women of child-bearing potential will be required to take a monthly urine pregnancy test and be on an agreed upon contraceptive. Participants will be randomized into one of two groups, a control group (receiving placebo medication) and an experimental group (receiving oral Oxandrolone, 12 mg twice daily for men and 6 mg twice daily for women for 12 weeks). Dosing will begin at the time of surgery and continue for 12 weeks, with medication dispensed by the USC Pharmacy. The study will be double-blinded: neither the treating surgeon nor the patient will know to which group the patient is enrolled.

Surgical Procedure

Arthroscopic inspection of the shoulder will be performed to verify the presence of a rotator cuff tear and to measure the size of the tear. In all cases a standard arthroscopic double-row technique will be used to repair the rotator cuff tendon.^{19,20} Treatment of the biceps tendon, need for subacromial decompression, and/or acromioclavicular joint resection will be at each surgeon's discretion. Intraoperative measurements of rotator cuff tear type and size as well as the details of the surgical procedure will be recorded.

Postoperative Rehabilitation

All participants in the study will undergo a standardized rehabilitation protocol for rotator cuff repair as agreed upon by the surgeons involved. Rehabilitation will be supervised by a licensed physical therapist. Adherence to the rehabilitation protocol will be assessed by review of patient treatment logs. If there are alterations to the standard postoperative rehabilitation course, the treating surgeon will be notified and will determine if the alteration in course warrants removal from the study. Patients who do not meet 80% adherence to the standardized protocol will be considered non-compliant and controlled for in the data analysis.

Feasibility

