5.0 Selection and Randomization of Subjects

Participants

Men and women, aged 40-75 years, presenting to an orthopaedic surgeon with a full thickness rotator cuff tear will be eligible for study screening. The inclusion and exclusion criteria are listed below.

All eligible patients will receive information about the trial verbally and in writing. After signing written informed consent, they will be randomly allocated to undergo rotator cuff repair followed by standard of care structured rehabilitation with Oxandrolone administration or standard of care structured rehabilitation with placebo. Allocation will be performed using computer software and will occur at the pharmacy to ensure that all investigators are blinded. The USC Pharmacy will prepare sequentially numbered, opaque, sealed envelope containing the assigned interventions to ensure randomness is preserved. The surgeon, PI, study team, and physical therapist will not know to which study arm the patient was randomized. The protocol for rehabilitation will remain the same for all patients. The USC Pharmacy will provide the investigators with a list of all participants and group assigned at the end of the study. Investigators will not have access to the study group assignment for any participant during data collection, to ensure adequate double-blinding of both the investigators and participants.

Inclusion criteria

- Men and women age 40-75 years old who have failed nonoperative management of chronic, full thickness rotator cuff tears confirmed by MRI without contrast

Exclusion criteria

- Patients with prior shoulder surgery or prior rotator cuff repair
- Tears larger than 5cm
- Significant glenohumeral arthritis (Hamada Grade 2 or higher)
- Untreated diabetes mellitus
- Pituitary tumor
- Rheumatoid Arthritis
- Uncontrolled hypertension
- Congestive Heart Failure
- Myocardial Infarction within the past 6 months

- End-stage renal disease
- Liver enzymes two times the normal value
- DVT within the past 6 months
- Disorder of the coagulation system
- Currently taking anticoagulation
- Claustrophobia
- Prior or current use of anabolic steroids
- Chromosomal disorders
- Prostate cancer
- Breast cancer
- Hypercalcemia
- Medications that interfere with testosterone production or function, including but not limited to 5 α -reductase inhibitors

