6.0 Study Agent Administration and Safety

Oxandrolone Administration

Oxandrolone will be given to experimental men (12 mg BID) and women (6 mg BID) for 12 weeks starting the day of surgery. Previous clinical studies where oxandrolone was given for greater than 6 months have shown no androgenic effects, behavioral changes, sepsis, hirsutism, or acne in the patient population. Elevated liver transaminase levels have been noted but have been transient and asymptomatic.¹⁻³

Patient Safety and Compliance

Patients will have liver transaminase levels measured when preoperative labs are obtained. Additionally, liver enzymes will be assessed at 2, 6, 12, and 24 weeks after rotator cuff repair. Testosterone levels and a quantitative assay for oxandrolone will also be drawn prior to supplementation, at the 2 week post-operative visit and at the 6 month post-operative visit to assess for compliance. Any adverse medication reaction will be met with cessation of medication, but will continue to be followed for outcome data collection.

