7.0 Clinical and Laboratory Evaluations

Program Time Line

Study participants will be tested on multiple occasions. Information will be collected prior to surgery, followed by measurements on the day of procedure, and 2, 6, 12, 24, 52, and 104 weeks after surgery. Surgery will be performed on an arranged date with the orthopaedic surgeon. Physical therapy will follow a pre-defined protocol with a physical therapist.

Testing Visits

Outcome measures and safety measures will be collected at routine postoperative visits with the operating surgeon. Dates and involved events are described in Table 1 below.

Schedule of Events

Event	Pre-Procedure	Procedure Day	Post-Operative Week					
			2	6	12	24	52	104
Informed Consent	x							
Demographics	x							
Confirm Inclusion/Exclusion Criteria	x	x						
Medical History	x	x						
Vital Signs	x	x	x	x	x	x	x	x
Randomization		x						
Blood draw: Testosterone level and Oxandrolone level	x		x			x		
Blood draw: Liver Enzymes	x		x			x	x	x
Outcomes:								
MRI: rotator cuff healing; Sugaya classification (primary outcome)	x				x		x	x
MRI: Fatty infiltrate (secondary outcome)	x				x		x	x
MRI: Muscle volume (secondary outcome)	x				x		x	x
Body Composition – lean mass & body fat (secondary outcome)	x		x	x	x	x	x	x
Questionnaires: ASES, VAS, PASS (secondary outcome)	x	x	x	x	x	x	x	x
Shoulder Range of Motion (secondary outcome)	x	x	x	x	x	x	x	x
Shoulder Strength (secondary outcome)	x	x	x	x	x	x	x	x

Table 1. Outline of pre- and postoperative timing of events and schedule of data collection.

Demographics.

Demographics of age, height, weight, race, arm dominance, and tear size and location will be recorded.

Inclusion and Exclusion Criteria.

The inclusion and exclusion criteria will be confirmed prior to enrolled, as described above in section 5.0.

Females of reproductive potential (women who have not been post-menopausal for at least 24 consecutive months, ie, who have had menses within the preceding 24 months, or women who have not undergone surgical sterilization, hysterectomy or bilateral salpingectomy or bilateral oophorectomy or tubal ligation) must have a negative serum or urine pregnancy test *with a sensitivity of ≤ 25 mIU/mL* within 48 hours prior to study entry.

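### The sample size credits the pre-randomization MRI with a treatment effect, and section 10.0 does not say how baseline Sugaya grade enters the primary GEE

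*Combined protocol and SAP*

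**What the plan says.** - **Analysis (section 10.0, Statistical Methods).** "Comparison for the primary outcome measure of rotator cuff integrity between groups from baseline to 1 year (primary endpoint) will be performed" by a repeated-measures GEE for ordinal data. No link, model terms, tested contrast or baseline covariate is given, and the arms are not constrained to be equal at baseline. No other section fills these gaps.
- **Sample size (section 10.0, Power Analysis).** The target is 1 Sugaya grade, SD 2, correlation 0.7, two-sided 0.05 and 80% power, "using 3 repeated measurements (baseline, 12 week, and 6 months", giving 104 participants. "This corresponds to an ANOVA effect size of 0.28".
- **Timing.** Table 1 in section 7.0 puts the first scan on the line "MRI: rotator cuff healing; Sugaya classification (primary outcome" at the pre-procedure visit and randomization on the procedure day. Section 6.0 gives drug "for 12 weeks starting the day of surgery".
- **Eligibility (section 5.0).** Entry requires "chronic, full thickness rotator cuff tears confirmed by MRI without contrast". Section 7.0 reserves Sugaya types IV and V for discontinuity that suggests a full-thickness tear.
- **Primary time point.** Section 8.0 says "The primary end-point will be 6 months", as does section 2.0; section 10.0 says 1 year. Table 1, as it reads, has MRI at weeks 12, 52 and 104 but not week 24.
- **Adherence (section 3.0, Postoperative Rehabilitation).** "Patients who do not meet 80% adherence to the standardized protocol will be considered non-compliant and controlled for in the data analysis".

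**The concern.** The baseline scan precedes randomization and drug, so any arm difference there is chance. Yet the planning calculation counts it as one of three measurements that carry the effect, and the analysis sentence starts its comparison from the same visit. The natural reading is that baseline Sugaya grade is one of the responses.

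Two costs could follow. A group effect averaged over all visits mixes in a visit with zero expected effect, so both the estimate and the real power fall below what the plan states. A group-by-time contrast instead subtracts a baseline difference that is only noise. Baseline grade would do more as a covariate. Adherence to rehabilitation is a separate matter: it is observed after randomization and may be affected by treatment, so adjusting for it can distort the randomized comparison.

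**Working it through.** **Inputs.** From section 10.0: difference 1 grade, SD 2, correlation 0.7, 52 per arm, two-sided 0.05. Powers are from noncentral t (equivalently F).

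**1. Reproduce the plan.** For one visit, f = (1/2)/2 = 0.25. Averaging m visits multiplies the variance by (1 + (m − 1) × 0.7)/m.

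| Visits averaged, 1 grade at each | Variance factor | f | Power at 104 |
|---|---|---|---|
| 3, baseline included | 2.4/3 = 0.80 | 0.25/√0.80 = 0.2795 | 80.6% |
| 2, post-baseline | 1.7/2 = 0.85 | 0.271 | 78% |
| 1 | 1.00 | 0.25 | 71% |

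Only the first row gives 0.28. It also gives 104, since power at 102 is 79.8%.

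**2. Set the baseline effect to zero, keeping SD 2 at every visit.** The averaged difference is (0 + 1 + 1)/3 = 0.667 grade. The standard error is √(4 × 0.80 × 2/52) = 0.351. Power is 46.9%, and 80% would need 114 per arm. With four visits (baseline, 12 weeks, 6 months, 1 year) the averaged difference is 3/4 of a grade.

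**3. Use a baseline that eligibility allows.** On types IV and V alone the SD is at most 0.5. Assuming 65% type V, it is √(0.65 × 0.35) = 0.48. Let r be the correlation of baseline with follow-up, which is not in the documents. The variance of the three-visit mean is [0.48² + 4 + 4 + 2 × 0.7 × 4 + 4 × r × 0.48 × 2]/9. The post-baseline mean has variance 4 × 0.85 = 3.40 unadjusted and 3.40 − 4r² adjusted for baseline. A single visit has 4 and 4(1 − r²).

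| | r = 0 | r = 0.3 | r = 0.6 |
|---|---|---|---|
| Variance of three-visit mean | 1.537 | 1.665 | 1.793 |
| Power, three-visit group effect (0.667 grade) | 78% | 74% | 71% |
| Power, post-baseline mean, unadjusted | 78% | 78% | 78% |
| Power, post-baseline mean, adjusted | 78% | 83% | 95% |
| Power, one visit, unadjusted | 71% | 71% | 71% |
| Power, one visit, adjusted | 71% | 75% | 88% |

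**4. Group-by-time, linear scale.** With SD 2 and correlation 0.7 throughout, change from baseline has variance factor 0.45 against 0.36 for covariate adjustment (post-baseline mean): power 96% against 99%. At 6 months alone the factors are 0.60 and 0.51: 90% against 94%. With the type IV/V baseline, the 6-month change has variance 4 + 0.48² − 2 × r × 0.48 × 2, and power is 69/75/82% against 71/75/88% adjusted. The cost is about 0 to 6 points.

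**5. Ordinal scale, by simulation.** A cumulative-logit GEE was run with 4,000 trials per setting, 52 per arm, and visits at baseline, 12 weeks and 6 months. Assumptions outside the documents are an odds ratio of 2.8, 30% large tears, 65% type V at baseline, re-tear of 40%/70% or 20%/40%, and r of 0, 0.3 or 0.6.

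- The all-visit group effect is diluted on the log-odds scale from 1.00 to 0.88 and from 1.03 to 0.87, that is by 12 to 16%.
- Moving from that test to the baseline-adjusted post-baseline mean gains 2 to 14 points. Moving to a baseline-adjusted 6-month test changes power by −5 to +8 points.
- Moving from group-by-time to the baseline-adjusted 6-month test gains 8 to 21 points, or 2 to 15 points if the effect is a full grade.
- Adding tear size beyond baseline grade gains about 0 to 2 points.

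**The case against.** The strongest reply is that section 10.0 does not write out the model. The phrase about baseline to 1 year may describe only a follow-up window, and a visit count in a planning formula does not bind the analysis. A visit-specific contrast at 6 months, or a model that keeps baseline as a response with its means constrained equal, would avoid both costs. This stands: baseline as a free response is an inference, though the natural one, and the two costs do not exhaust the possibilities. The plan specifies neither alternative.

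A reader might also infer that the trial has only 47% power. The documents do not support that. The figure needs a baseline SD of 2, and full-thickness eligibility confines baseline to two adjacent grades. With a realistic baseline, including it costs 0 to 7 points against the unadjusted post-baseline mean.

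Nor can one infer that the comparison is biased for want of a covariate. Omitting baseline covariates does not bias a randomized comparison, and group-by-time is unbiased as well. The two-thirds dilution belongs to the grade scale; an ordinal model reports log-odds, where it is smaller. The large ordinal losses for group-by-time rest on inputs that the documents do not give.

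Finally, a single-visit test is not always the more powerful choice. It gives up averaging, and it lost power in some simulated settings.

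**Conclusion.** The concern holds in a limited form. What is firm is that the stated 104 and 0.28 assume a 1-grade difference at a scan taken before randomization and drug, and that the plan states neither the tested term nor the role of baseline. The claimed 80% is therefore not the power of any contrast confined to visits where an effect can exist. On the plan's own SD and correlation, without adjustment, 52 per arm gives 78% for the two-visit post-baseline mean and 71% for one visit.

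If the all-visit group effect is tested, power is about 71 to 78%, assuming a baseline SD of about 0.5 and a baseline correlation of 0 to 0.6, and the estimate is diluted. If group-by-time is tested, the linear-scale cost is small, and any larger ordinal cost is conditional on outside assumptions. This is a matter of specification and efficiency that merits correction before unblinding; it is not a flaw that invalidates the trial.

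**What to change.** In section 10.0:

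1. Model only the post-baseline Sugaya grades as the response, with baseline Sugaya as a covariate fixed before unblinding. Tear size is optional. State the link.
2. Name the tested arm contrast. It can be the single primary time point, once sections 2.0, 8.0 and 10.0 and Table 1 are reconciled on 6 months or 1 year and on the week-24 MRI. It can instead be the mean over post-baseline visits. Note that a single-visit test can lose power relative to averaging.
3. Recompute and restate power for that contrast without counting baseline as a visit that carries the effect. Give a range over the baseline correlation.
4. Report the unadjusted post-baseline result beside the adjusted one.
5. Keep rehabilitation adherence (section 3.0) out of the primary model and use it only in a labelled sensitivity analysis.

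The cost is a few sentences and one recalculation; using baseline as a covariate needs no new data. The odds ratio becomes conditional on the covariate, and a degree of freedom is used. On the logit scale, the gain from adjustment comes from a larger conditional odds ratio rather than a smaller standard error.

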2.0 Objectives and Purpose

Specific Aim #1. Determine if oral Oxandrolone administration will improve rotator cuff healing following rotator cuff repair.

Oxandrolone is an orally administered synthetic derivative of testosterone that is approved by the Federal Drug Administration (FDA) in patients who have lost weight resulting from extensive surgery, severe trauma, chronic infection, or as an adjunctive therapy to promote weight gain. It is also approved for bone pain associated with osteoporosis, and to attenuate protein catabolism associated with the prolonged use of corticosteroids. Oral administration of Oxandrolone has demonstrated increases in lean mass, protein synthesis, and wound healing with no long-term adverse events in trauma patients as well as healthy male controls.¹⁻³ The aforementioned safety and efficacy profile of oral Oxandrolone makes it an appealing adjuvant treatment to counteract the major biologic consequences of a chronically torn rotator cuff (muscle atrophy, fatty infiltration, and intercellular fibrosis), which are known to lead to poor healing and diminished clinical outcomes.^{4,5} The primary aim of this double-blind, randomized study is to compare the rotator cuff healing rates between an experimental group receiving 12 weeks of daily, orally administered Oxandrolone following rotator cuff repair to a control group undergoing the same rotator cuff repair and receiving 12 weeks of a daily, orally administered placebo medication. The healing spectrum from complete healing to re-tear will be defined based on a previously validated diagnostic imaging metric. The primary outcome measure is rotator cuff muscle-tendon structural healing as measured by the Sugaya classification on magnetic resonance imaging (MRI) at the primary end-point of 6 months.⁶ We will continue to follow for one year. We hypothesize that those in the experimental group (Oxandrolone group) will have greater rotator cuff tendon structural healing as compared to the control (Placebo group) at the primary end-point of 6 months post-operative.

The secondary measure of healing will be the degree of fatty infiltration of the muscle-tendon unit on MRI using the Goutallier grading classification.⁷ We hypothesize that those in the experimental group (Oxandrolone group) will have less fatty infiltrate as compared to the control (Placebo group) at primary end-point of 1 year.

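### The sample size calculation counts the pre-treatment baseline as an outcome visit, so its 80% is not the power of the 6-month comparison; and its 28% of variance should be about 7%

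*Combined protocol and SAP*

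**What the plan says.** Section 10.0 (Power Analysis and Sample Size) sets out to detect one Sugaya grade with two-sided alpha 0.05 and 80% power, "using 3 repeated measurements (baseline, 12 week, and 6 months"), "assuming a correlation among the repeated measures of 0.7 and overall SD of 2". The result is 104 participants, 52 per group, raised to 116 for 10% attrition. The paragraph then translates the assumption into an "ANOVA effect size of 0.28 (28% of variance in primary outcome explained by treatment effect") and, alternatively, into a Cohen's d of 0.5.

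Section 3.0 fixes when treatment starts: "Dosing will begin at the time of surgery and continue for 12 weeks". Specific Aim 1 in section 2.0 places the primary outcome on "magnetic resonance imaging (MRI) at the primary end-point of 6 months", and section 8.0 agrees: "The primary end-point will be 6 months". The Statistical Methods text of section 10.0 instead describes a GEE comparison "between groups from baseline to 1 year (primary endpoint"). Section 8.0 lists the Sugaya measure at 12 weeks, 6 months, 1 year and 2 years. In Table 1 of section 7.0, as it reads in the extracted text, the row "MRI: rotator cuff healing; Sugaya classification (primary outcome") has marks at pre-procedure and weeks 12, 52 and 104, and none at week 24.

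**The concern.** Averaging repeated measurements gains power when each of them carries the treatment effect. A pre-treatment measurement carries none. It can serve as a covariate or as the reference for a change score, but each use has its own variance formula and neither is the one applied here. If the 80% belongs to an average that includes baseline, it does not describe the 6-month comparison on which the trial is to be judged, and a reader cannot take from it what 6-month difference 52 evaluable patients per arm can detect.

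Separately, a treatment that explains 28% of the variance would be a far larger effect than a d of 0.5, so the two descriptions offered in the same sentence cannot both be right.

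**Working it through.** **Inputs, all from section 10.0:** difference δ = 1, SD σ = 2, correlation ρ = 0.7, m = 3 measurements, two-sided α = 0.05, 52 per arm. Like the plan's own calculation, everything below treats the grade as continuous.

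**1. Reproducing N = 104.** With equal correlations, the mean of m visits has variance σ²(1 + (m − 1)ρ)/m. For m = 3 the factor is (1 + 2 × 0.7)/3 = 0.80. Cohen's f at one visit is δ/(2σ) = 0.25; for the three-visit mean it is 0.25/√0.80 = 0.2795, which is the plan's 0.28. The noncentral F test (1 and N − 2 df, noncentrality N f²) gives 79.8% at N = 102 and 80.6% at N = 104. The smallest even N reaching 80% for other values of m is:

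| m | 1 | 2 | 3 | 4 | 5 |
|---|---|---|---|---|---|
| N | 128 | 110 | **104** | 100 | 98 |

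Only m = 3 returns 104, so baseline was credited as a visit with a full one-grade difference. The attrition step also reproduces: 104/0.9 = 115.6, or 116.

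**2. Power of analyses the trial could run, at the stated inputs** (noncentral t, 52 per arm, δ = 1):

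| Analysis | SD used | Power |
|---|---|---|
| 6 months, unadjusted | 2 | 71% |
| Mean of 12 weeks and 6 months | 2√0.85 = 1.84 | 78% |
| 6-month change from baseline | 2√(2(1 − 0.7)) = 1.55 | 90% |
| 6 months, baseline as covariate | 2√(1 − 0.7²) = 1.43 | 94% |

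If the GEE averaged a null baseline into the treatment effect, the difference in the three-visit mean would be (0 + 1 + 1)/3 = 2/3 grade, and power 47%. The plan gives no model terms, so this last figure is conditional.

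**3. The baseline inputs.** Section 5.0 admits only full-thickness tears, and section 7.0 describes full-thickness tears under Sugaya types IV and V. A variable confined to 4 and 5 has an SD of at most 0.5, so SD 2 cannot hold at baseline. With baseline SD 0.5 and 6-month SD 2, the change score has variance 4 + 0.25 − 2ρ × 2 × 0.5. Correlations of 0.5 and 0.3 are assumptions added here to show the range:

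| ρ, baseline to 6 months | 0.7 | 0.5 | 0.3 |
|---|---|---|---|
| Change score | 85% | 80% | 75% |
| Baseline as covariate | 94% | 83% | 75% |

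**4. The SD at follow-up.** On a 1–5 scale with mean μ, the SD cannot exceed √((μ − 1)(5 − μ)). This is 2.0 at μ = 3, with every patient at grade I or V. For two arms one grade apart, the largest common within-arm SD is √(1.5 × 2.5) = 1.94, at means 2.5 and 3.5. The plan's SD of 2 is thus at the ceiling and conservative. For the plain 6-month comparison at 52 per arm:

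| SD | 1.94 | 1.8 | 1.75 | 1.4 | 1.2 |
|---|---|---|---|---|---|
| Power for 1 grade | 74% | 80% | 82% | 95% | 99% |

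The difference detectable with 80% power is 1.00 grade at SD 1.8, 0.78 at SD 1.4 and 0.67 at SD 1.2.

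**5. Variance explained.** The proportion is f²/(1 + f²). For f = 0.28 it is 0.0784/1.0784 = 7.3%. For f = 0.25, a single visit, it is 0.0625/1.0625 = 5.9%. A true 28% needs f = √(0.28/0.72) = 0.62. The stated figure is too large by a factor of 28/7.3 = 3.8.

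**The case against.** The strongest reply is that little follows in practice. The figures of 71% and 78% rest on an SD of 2, which cannot hold in both arms. At the feasible ceiling of 1.94, the unadjusted 6-month test has 74%, and the mean of the two post-operative visits has 80.8%. Dropping baseline from the plan's own averaging would therefore still leave 80% at any feasible SD, if the correlation of 0.7 holds. The paragraph also states the difference, the SD and d = 0.5 correctly, and the variance gloss does not enter N. Finally, the declared analysis is an ordinal GEE over repeated visits, not a two-sample test at 6 months.

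Much of this stands, and it is why no claim of underpowering is made. It does not rescue the stated basis. The post-operative mean is not the 6-month end-point that sections 2.0 and 8.0 name. The 80% matches none of the 6-month analyses at the inputs from which it was derived. Power for an ordinal GEE cannot be computed from the documents, which give no category probabilities; the plan's own calculation is on the continuous scale too, so the comparison is like with like. The replacement variance figure does depend on the target: about 7% for the three-visit mean, about 6% for one visit.

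**Conclusion.** The concern holds. The stated 80% is the power of a test on a three-visit mean that includes baseline and assumes a treatment difference there. At the plan's inputs the 6-month comparison has between 71% and 94% power depending on the analysis, and the plan does not specify the model closely enough to choose among them. The 28% misreads Cohen's f as a proportion and overstates the assumed effect nearly fourfold.

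The direction of the power error is open. An unadjusted comparison falls short of 80% for SDs above about 1.8 and exceeds it below; a baseline-adjusted one depends on a correlation the documents do not support separately. These results rest on the continuous-scale approximation, on 52 evaluable patients per arm and, for the baseline SD limit, on reading eligible full-thickness tears as types IV and V. The missing week-24 MRI mark rests on a table that extraction may have damaged. The conflict between 6 months and 1 year does not depend on that table.

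**What to change.** 1. Settle one primary time point. Reconcile sections 2.0 and 8.0 (6 months) with the Statistical Methods text of section 10.0 (1 year), and check that Table 1 schedules the MRI at the chosen visit.
2. Restate power for the between-group comparison at that time point, without counting baseline as an outcome. Use a range of SDs below 1.94, labelled as assumptions; the detectable differences in step 4 of the working can be used directly for an unadjusted comparison. State that the calculation treats the ordinal grade as continuous.
3. If baseline enters as a covariate, say so in the model and give its assumed correlation with follow-up separately from the correlation between follow-up visits.
4. Replace 28% of variance with about 7% and say that f = 0.28 refers to the three-visit mean. If power is restated for a single visit, use f = 0.25 and about 6%. The d of 0.5 is correct for the stated inputs; update it if the SD changes.

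The cost is one rewritten paragraph and one agreed time point, with enrolment left at 116. If the sponsor keeps SD 2 and an unadjusted 6-month comparison, the stated power must fall to 71%.
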